Gout (SCRI)	M10.x, M1A.x (chronic gout)	PPV: 61% (≥ 2 visits associated with the diagnosis) ¹⁵	At least one gout- specific oral medication (allopurinol, colchicine, probenecid, febuxostat) prescribed within 3 months after the first date of the diagnosis.	≥2 outpatient claims within the follow-up windowa OR ≥1 inpatient claim	Days 1-30	1 year; diagnosis code –all settings ^b OR At least one gout- specific oral medication (allopurinol, colchicine, probenecid, febuxostat);	Same as in Col. 2 OR Col. 4	HOI	-Exclude chronic and secondary gout codes. -Examine frequency distribution of ICD-10 codes and consider low- frequency codes such as codes for chronic gout (M1A*), lead- induced gout (M10.1*, drug-induced gout (M10.2*), and gout due to renal impairment (M10.3*) (note: this exclusion of gout codes does not apply in assessing prevalent gout) ^d

209696 (EPI-ZOSTER-032 VS US DB) Protocol Amendment 3 Final

1	2	3	4	5	6	7	8	9	10
Study Outcome (Study design)	ICD-10 code(s) for case ascertainment	Validation Statistics	Other requirements ^c	Setting for case ascertainment	Risk Interval	Look-back period & settings to determine incidence	What to look back for	What to look back from	Sensitivity Analysis
PMR (Cohort)	M35.3 – PMR M31.5 – GCA w/ PMR	Sensitivity: 99.5% Specificity: 92.2% ¹⁶ (based on the 3 methods used by Bernatsky: diagnosis in inpatient or outpatient, or a visit by a rheumatologist/ internist)	2 oral glucocorticoids (cortisone, dexamethasone, hydrocortisone, methylprednisolone, prednisolone, prednisone) prescriptions; The first dispensing within 6 months of PMR diagnosis and the second dispensing date within 6 months after the first dispensing.	≥2 outpatient claims within the follow up window a OR ≥1 inpatient claim	Days 1-183	1 year; all settings⁵	Same as in Col. 2	Exposure	N/A
GCA (Cohort)	M31.6 (GCA), M31.5 (GCA with PMR), M31.9 (necrotizing vasculopathy unspecified)	Not available	2 oral glucocorticoids (cortisone, dexamethasone, hydrocortisone, methylprednisolone, prednisolone, prednisone). The first dispensing within 6 months of GCA diagnosis and the second dispensing date within 6 months after the first dispensing.	≥2 outpatient claims within the follow up windowª OR ≥1 inpatient claim	Days 1-183	1 year; all settings⁵	Same as in Col. 2	Exposure	-Use the primary algorithm based on the GCA diagnosis code and steroid prescription but ADD a requirement for a temporal artery biopsy at the time of diagnosis, as determined by a CPT code=37609

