9.3.4. Potential confounding variables and effect modifiers

A confounder is defined as any variable that is associated with both the exposure and the study HOI. Since a confounder cannot be on the causal pathway from exposure to the outcome, all confounders will be captured in the 365 days preceding the index date, i.e., RZV Dose 1 and Dose 2 vaccination date and the RZV unvaccinated comparator preventive care visit for the cohort design. All confounders identified using Medicare enrollment and medical or prescription claims data will be used for covariate adjustment in multivariable models. Propensity score methods will be considered for confounding adjustment, depending on identified imbalances in the observed covariates between the exposed and comparator groups. Confounding variables defined by health care services and comorbidities will be identified using a combination of ICD-10, CPT and HCPCS codes.

- **Demographic variables** will include age, sex, and race and ethnicity (i.e., white, black, Asian, Hispanic, North American Native, and other/unknown based on the US government categories)
- **Healthcare service variables** will include admissions to skilled nursing facilities (SNFs), number of hospitalizations, number of ED visits and Durable Medical Equipment (DME) use. These will be considered to control for potential imbalances between RZV vaccinees and RZV unvaccinated comparators in health impairment requiring more intensive services. The place of service and revenue code on the claim are used to designate the type of service setting.
- **Preventive care services** will include receipt of age-recommended vaccine (e.g., influenza, pneumococcal, and tetanus, diphtheria, pertussis). These will be

considered to control for potential healthy adherer bias that could result in imbalances in healthcare services and prior health seeking behavior patterns between RZV vaccinees and RZV unvaccinated comparators. Table 2 lists the preventive care services. Since mammography, bone mineral density, and colorectal screening are criteria for the unvaccinated comparator selection, these are not included as confounders in the analysis.

- **Medical comorbidities specific to PMR/GCA**. Potential risk factors specific to these conditions may include:
 - Age, which is found to be the strongest risk factor;¹⁹
 - Female sex is found to be a risk factor;¹⁹
 - Race/ethnicity as a significantly lower incidence is reported in African, Asian, Latinos;¹⁹

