 - Gout has been associated in a few studies (from same group using CMS data);^{20,21}
 - Prior hematologic malignancy has conflicting results on the association, but has been shown in some studies;²²
 - Case reports/series with use of checkpoint inhibitors show development of PMR or PMR-like syndrome;²³
 - Immunocompromising conditions, given that PMR is an immune-mediated disorder, potentially imbalance in T-regulatory lymphocytes and proinflammatory T-helper 17 cells.
- **Medical comorbidities specific to ION**. Risk factors specific to ION include:²⁴⁻²⁸
 - Arteritic ION is significantly less common than non-arteritic and is strongly associated with GCA, thus we will consider similar risk factors/potential confounders.
 - Non-arteritic ION Anterior Ischemic Optic Neuropathy has reported associations with obstructive sleep apnea, vasculopathic/ prothrombotic conditions (e.g., diabetes, hypertension, spinal and cardiac surgery, some medications (amiodarone, phosphodiesterase type 5 inhibitors).
- **General medical comorbidities**. Other comorbidities or chronic conditions may be important to address confounding by indication, e.g., relatively common conditions that are indicative of functional status or illness severity.
 - Diabetes mellitus
 - Chronic kidney disease
 - Chronic lung disease chronic obstructive pulmonary disease and chronic bronchiectasis
 - Congestive heart failure
 - Ischemic heart disease
 - Dementia Alzheimer's Disease and Related Disorders or Senile Dementia

- Chronic liver disease cirrhosis and other liver conditions except hepatitis
- Stroke/Transient Ischemic Attack
- **Immunocompromised conditions**. This includes solid organ transplant, hematopoietic cell transplant, hematologic or solid malignancy with recent receipt of chemotherapy, autoimmune/inflammatory condition *or* on an immunosuppressive regimen, and human immunodeficiency virus infection.

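### Apart from M31.5, the PMR and GCA look-backs do not search each other's codes, and prior PMR or GCA is not a named covariate for PMR, GCA or ION

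*Combined protocol and SAP*

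**What the plan says.** Table 3 (9.3.2) gives the PMR case codes as "M35.3 – PMR M31.5 – GCA w/ PMR" and the GCA case codes as "M31.6 (GCA), M31.5 (GCA with PMR), M31.9 (necrotizing vasculopathy unspecified". For both outcomes the look-back is one year, in all settings, from the index date, and searches for "Same as in Col. 2". Section 9.1 applies the baseline exclusion outcome by outcome.

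Both outcomes also need two oral glucocorticoid prescriptions. For PMR: "The first dispensing within 6 months of PMR diagnosis and the second dispensing date within 6 months after the first dispensing". For GCA: "The first dispensing within 6 months of GCA diagnosis and the second dispensing date within 6 months after the first dispensing". Neither look-back searches for these drugs. The gout row differs on both counts: its look-back is "Same as in Col. 2 OR Col. 4", so it includes the drugs, and the gout drug must follow the first diagnosis date.

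Section 9.3.4 introduces the PMR/GCA covariates with "Potential risk factors specific to these conditions may include" and lists age, sex, race/ethnicity, gout, hematologic malignancy, checkpoint inhibitors and immunocompromising conditions. For ION it says: "Arteritic ION is significantly less common than non-arteritic and is strongly associated with GCA, thus we will consider similar risk factors/potential confounders". Prior PMR and prior GCA are not named in either list. A composite of immunocompromised conditions covers autoimmune or inflammatory disease and immunosuppressive regimens, without a code list. On selection, 9.3.4 adjusts for all identified confounders, while 9.7.10 adjusts for variables whose standardized mean difference (SMD) exceeds 0.10.

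**The concern.** The plan itself treats PMR and GCA as overlapping: they share code M31.5 and have the same steroid rule. Yet a person already coded and treated for one can enter the analysis of the other as disease-free.

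Two things follow. First, classification. A patient on steroids for M31.6 whose later claims carry M35.3 or M31.5 becomes a PMR event. A patient on steroids for M35.3 may already satisfy the GCA steroid criterion, so that two outpatient GCA claims, or one inpatient claim, complete the definition. Second, confounding. If prior PMR or GCA is more or less common among vaccinees, and strongly predicts the other disease or ION, the hazard ratio shifts unless the model contains it.

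An imbalance is plausible. The recommendation cited in section 7 is for immunocompetent adults, so treated PMR or GCA could be rarer among vaccinees, which would pull the hazard ratio down in a safety study. The documents do not quantify this, and the opposite direction is possible.

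**Working it through.** **1. Codes side by side (Table 3)**

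| Baseline code only | PMR analysis | GCA analysis |
|---|---|---|
| M35.3 | excluded | retained |
| M31.5 | excluded | excluded |
| M31.6 | retained | excluded |
| M31.9 | retained | excluded |

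**2. The plan's own figures.** Table 5 reproduces with a Poisson-regression formula, exposed fraction π = 0.2 and T = 0.5 year:

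N = [1.96·√(1/(π(1−π))) + 0.8416·√(1/(1−π) + 1/(π·RR))]² / (T·rate·(ln RR)²)

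- PMR, rate 0.000405, RR 2: 438,239 (plan 438,239).
- GCA, rate 0.000092, RR 3: 723,361 (plan 723,362).

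These sizes are not in dispute. They show that the rates act as annual rates over half a year.

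**3. Precision at the planned size.** Section 9.2.2 projects about 2 million vaccinees and 8 million comparators. Under no effect:

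- PMR events: 2,000,000 × 0.000405 × 0.5 = 405, and 1,620 in comparators. 95% factor exp(1.96·√(1/405 + 1/1620)) = 1.12.
- GCA events: 2,000,000 × 0.000092 × 0.5 = 92, and 368 in comparators. 95% factor exp(1.96·√(1/92 + 1/368)) = 1.26.

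**4. Shift in a null GCA hazard ratio, by share of events (assumed).** Let f be the share of GCA events arising in people with baseline PMR, and d the vaccinee-to-comparator ratio of baseline PMR prevalence. HR = f·d + (1 − f).

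| f | d = 0.8 | d = 1.0 | d = 1.2 |
|---|---|---|---|
| 10% | 0.98 | 1.00 | 1.02 |
| 30% | 0.94 | 1.00 | 1.06 |
| 50% | 0.90 | 1.00 | 1.10 |

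**5. The same shift, by prevalence (assumed).** With comparator prevalence p0, vaccinee prevalence p1 and relative hazard R: HR = [1 + p1(R−1)] / [1 + p0(R−1)].

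- Mild: p0 from 0.2% to 2%, p1/p0 from 0.8 to 1.25, R up to 10. The extremes are at p0 = 2%, R = 10: (1 + 0.016·9)/(1 + 0.02·9) = 0.97 and (1 + 0.025·9)/(1 + 0.02·9) = 1.04.
- Severe corner: p0 = 2%, a two-fold imbalance, R = 50: 0.75 to 1.50. This needs all three inputs to be high at once.

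**6. PMR (assumed).** Suppose prior GCA is rarer than prior PMR in the ratio of the Table 5 rates, 0.000092/0.000405 = 0.227, with the same relative hazard. For a rare condition the odds f/(1−f) scale by 0.227, so 30% and 50% become about 9% and 18%. At a 20% imbalance the null PMR hazard ratio is about 0.98–1.02 and 0.96–1.04. No size was computed for ION.

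**7. Would the SMD rule pick up a separate indicator?** SMD = (p1 − p0)/√{[p1(1−p1) + p0(1−p0)]/2}. For a doubling:

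| p0 | SMD |
|---|---|
| 0.2% | 0.037 |
| 0.5% | 0.058 |
| 1% | 0.082 |
| 2% | 0.117 |

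At 1% or less, an indicator twice as common in one arm would still miss 0.10. At 2% a doubling passes, but a ratio of 1.25 gives only 0.034.

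**The case against.** A reader might infer that the look-backs ignore the related disease altogether. They do not: M31.5 is in both lists and excludes from both analyses.

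A reader might infer that prior PMR and GCA go unadjusted. The documents do not establish that. The immunocompromised composite could contain these codes and long-term steroid use, the PMR/GCA covariate list is worded as open, and 9.3.4 promises adjustment for every identified confounder. What stands is narrower: without a code list the reader cannot tell, and a pooled indicator mixes PMR and GCA with conditions of different relevance. The bias analysis in 9.7.10 does not fill the gap, because it addresses unobserved confounders and this one is visible in the claims.

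A reader might infer that every retained patient is a false incident case. A first GCA code in someone with known PMR can be genuine new GCA, which is what the objective seeks, and incidence defined disease by disease is coherent. The steroid wording gives no direction in time, so counting earlier steroids is one reading of it. The GCA sensitivity definition requiring temporal artery biopsy (Table 3, 9.7.6) also tests for false GCA, although its inferential analysis depends on the case count. These points stand; they argue for adjustment and a sensitivity analysis over exclusion from the primary analysis.

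Finally, the plan argues in 9.9 that both arms use preventive care, and even the 0.90–1.10 GCA range lies inside the sampling factor of 1.26 and far from the target relative risk of 3. That limits the importance of the point, but does not make an avoidable bias worth keeping.

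**Conclusion.** The point holds as a low-cost improvement, not as an error in the plan. Related disease coded only as M31.6 or M31.9 (for PMR) or M35.3 (for GCA) passes the look-back, and steroids already taken for it are not ruled out as meeting the case definition. Prior PMR and GCA are not named covariates, and under 9.7.10 a separate rare indicator would usually be left out. Some already-treated related disease may therefore be counted as new onset, and any baseline imbalance would be only partly controlled.

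The size rests entirely on assumptions, because the documents give no prevalence, overlap or imbalance. A null GCA hazard ratio moves to about 0.97–1.04 under mild inputs, and to 0.90–1.10 if half of GCA events arise in people with baseline PMR and the imbalance is 20%. For PMR the shift is probably smaller; for ION it is not estimated. With no imbalance a null hazard ratio stays at 1.00, though misclassified events could still dilute a real effect. It would go too far to say that imbalance passes directly into the hazard ratios: that requires both an imbalance and no control through the composite, and the documents show neither.

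**What to change.** - In 9.7.10, force separate baseline indicators into the Cox models whatever their SMD: M35.3 for GCA; M31.6/M31.9 for PMR; PMR and GCA codes for ION.
- Add a sensitivity analysis of PMR and GCA that excludes anyone with a baseline code for either disease (M35.3, M31.5, M31.6, M31.9).
- State whether these codes belong to the autoimmune or inflammatory composite, and reconcile 9.3.4 with 9.7.10 on which covariates are adjusted for.

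The codes are already used in Table 3, so the cost is SAP wording and slightly more analysis work. A few events are lost, in the sensitivity analysis only; the primary populations and stated sample sizes do not change.

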209696 (EPI-ZOSTER-032 VS US DB)

Protocol Amendment 3 Final

1	2	3	4	5	6	7	8	9	10
Study Outcome (Study design)	ICD-10 code(s) for case ascertainment	Validation Statistics	Other requirements ^c	Setting for case ascertainment	Risk Interval	Look-back period & settings to determine incidence	What to look back for	What to look back from	Sensitivity Analysis
ION (Cohort)	H47.01	Not available	Exclude patients who had coronary artery bypass graft (CABG) surgery ¹⁷ or lumbar or lumbosacral spinal fusion and/or laminectomy surgery within 30 days before ION diagnosis date	≥1 claim in all settings	Days 1-183	1 year; all settings ^b ICD code only	Same as in Col. 2	Exposure	Additional criteria for arteritic: ≥ 40 mg/day of prednisone prescription ± 4 weeks of the diagnosis plus an ophthalmologist/neuro- ophthalmologist consult (if possible) and GCA diagnosis within 3 months; lookback to rule out prevalent cases will use ICD code only; all settings
SVT (SCRI)	147.1	Sensitivity-91.7% ¹⁸	None	≥1 ED or inpatient claim any position	Days 1-30	1 year; all settings ^b any position	Same as in Col. 2	HOI	N/A

Definitions: ALS - Amyotrophic Lateral Sclerosis; CVA - Cerebrovascular Accident; GCA - Giant Cell Arteritis; GSB - Guillain-Barré Syndrome; ION - Ischemic Optic Neuropathy; PMR - Polymyalgia Rheumatica; SCRI - Self-controlled Risk Interval; SVT - Supraventricular Tachycardia;

^a Outpatient visits are defined using ≥2 claims for consistency with methods used by CMS algorithms using the CMS CCW Medicare data to define chronic conditions, and to avoid misclassification of the outcome due to the potential for 1 visit to reflect rule-out diagnosis.

^b Includes inpatient, emergency department, and outpatient settings.

^c Based on external expert opinion.

^d Consistent with the study EPI-ZOSTER-030 VS US DB, no analysis will be conducted for the gout sensitivity HOI definitions. These definitions are for administrative purposes only .

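### Ischemic optic neuropathy (ION) is the only outcome that a single office claim can establish, and no planned analysis tests how specific the non-arteritic cases are

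*Combined protocol and SAP*

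**What the plan says.** All of this is in Section 9.3.2, Table 3, unless stated otherwise.

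- **ION, primary definition.** Code H47.01 on "≥1 claim in all settings". Validation statistics: "Not available". The only other requirement excludes patients with coronary bypass surgery or "lumbar or lumbosacral spinal fusion and/or laminectomy surgery within 30 days before ION diagnosis date".
- **Gout, PMR and GCA.** Each needs at least one inpatient claim or at least two outpatient claims (for PMR and GCA, "≥2 outpatient claims within the follow up window"), plus dispensing of specified drugs. Footnote a, attached to these cells, gives two reasons for the two-claim rule: consistency with the CMS algorithms for chronic conditions, and "to avoid misclassification of the outcome due to the potential for 1 visit to reflect rule-out diagnosis".
- **GBS and SVT.** GBS always needs an inpatient claim. SVT needs one emergency department or inpatient claim.
- **ION, sensitivity definition (column 10).** "Additional criteria for arteritic: ≥ 40 mg/day of prednisone prescription ± 4 weeks of the diagnosis", with a specialist consult if possible and a GCA diagnosis within 3 months. Section 9.3.4 states: "Arteritic ION is significantly less common than non-arteritic". Section 9.7.7 commits to counts and rates under this definition, with further analysis only if there are enough cases.
- **Validation.** Sections 9.4.2 and 9.9 say that charts cannot be reviewed. The ENCePP checklist, item 10.6, marks analytic control of outcome misclassification as not applicable.

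**The concern.** A diagnosis code on one office claim can record a suspicion that is later dropped. Footnote a names this risk for one visit and protects three outcomes against it. ION has no such protection, and the plan gives no reason for treating it differently.

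The introduction to Table 3 presents column 10 as the place for sensitivity analyses where no validated algorithm exists. GCA, which also lacks validation figures, gets a stricter definition there for the whole outcome (temporal artery biopsy). The ION entry tightens only the arteritic form.

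None of the other checks fills the gap. The COVID-19 analysis (Section 9.7.8) changes which exposures are included, and the bias analysis (Section 9.7.10) deals with unmeasured confounding. A hazard ratio near 1 for ION could mean no association, or an association diluted by non-cases, and the planned output could not help to separate the two.

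**Working it through.** **1. What one office claim can establish**

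| Outcome | Is one office claim enough? | Confirmation required |
|---|---|---|
| GBS | No | Inpatient claim |
| SVT | No | Emergency department or inpatient claim |
| Gout, PMR, GCA | No | Second outpatient claim or an inpatient claim, plus drug criteria |
| ION | Yes | None (surgical exclusions only) |

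**2. Figures in the plan.** There is no ION figure to reproduce: Table 6 gives no target risk, and no ION incidence, PPV or sample size is stated. The nearest figures are the PMR and GCA sizes in Table 5. With p = 0.2 exposed, T = 0.5 year, two-sided alpha 0.05 and 80% power, the Poisson regression formula is

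N = [1.96·√(1/(p(1−p))) + 0.84·√(1/(1−p) + 1/(p·RR))]² / (T·rate·ln(RR)²).

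It gives 723,361 for GCA at RR 3 (stated 723,362) and 438,239 for PMR at RR 2 (stated 438,239). This says nothing about ION, but it confirms the formula behind the last column in step 4.

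**3. Effect of false positives on the hazard ratio.** Let comparators have true-case rate λ and false-positive rate φ, so that PPV = λ/(λ+φ). Vaccinees have true-case rate HR·λ and false-positive rate f·φ. Then

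observed HR = PPV·HR + (1−PPV)·f.

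With f = 1 (equal false-positive rates) this becomes 1 + PPV·(HR−1).

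**4. Equal false-positive rates; PPV is an assumed range.** Events are from the Schoenfeld formula with 20% exposed: (1.96+0.84)² / (0.2·0.8·ln(observed HR)²). The cohort multiple uses the step 2 formula with the observed HR and a claim rate of λ/PPV.

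| PPV in comparators | True HR 2 reads | True HR 3 reads | Claim-defined events for 80% power, true HR 2 | Power with 103 claim-defined events | Cohort multiple, true HR 2 |
|---|---|---|---|---|---|
| 100% | 2.0 | 3.0 | 103 | 80.3% | 1.00 |
| 80% | 1.8 | 2.6 | 142 | 66.5% | 1.13 |
| 50% | 1.5 | 2.0 | 299 | 37.7% | 1.54 |
| 30% | 1.3 | 1.6 | 713 | 18.5% | 2.27 |

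The cohort multiple grows less than the event count because false positives also add events. A true HR of 1 stays at 1.

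**5. Unequal false-positive rates, PPV 50%, f from 0.5 to 2.**

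- True HR 1: 0.5·1 + 0.5·0.5 = 0.75, up to 0.5·1 + 0.5·2 = 1.5.
- True HR 2: 0.5·2 + 0.5·0.5 = 1.25, up to 0.5·2 + 0.5·2 = 2.0.

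Unequal rates are conceivable because one arm is indexed at a vaccination and the other at a preventive care visit. The documents do not say whether rule-out coding differs between them.

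**The case against.** The strongest opposing case is that a sensitive one-claim rule is a defensible choice for a rare secondary outcome, and that the plan is open about its limits. Footnote c says the additional requirements rest on expert opinion, Section 9.9 concedes that claims algorithms are rarely both sensitive and specific, and column 10 does contain an ION entry. All of that stands. It is why the one-claim rule can remain primary and why no primary conclusion of the study is affected.

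Four stronger readings are tempting, and the documents support none of them.

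- **That non-cases do dilute the ION hazard ratio.** No false-positive rate for ION is given, and bias toward 1 requires equal rates in both arms. Size and direction are both open.
- **That the plan contradicts itself.** Footnote a is not attached to the ION cell, and one of its two reasons concerns chronic-condition algorithms, a class in which the documents do not place ION. Its rule-out reasoning extends naturally to any single outpatient claim, but that is an inference.
- **That the PPVs in Table 3 show a single ION claim to be unreliable.** The 50% for GBS is for inpatient visits and the 61% for gout is for two or more visits. They concern other diseases and stricter rules, and they do not show that a two-claim ION rule would do better.
- **That a null ION result would be uninterpretable.** At an assumed PPV of 80%, a true HR of 2 still reads 1.8.

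A practical objection also stands. Section 9.3.2 requires both claims to fall within follow-up. Under that rule a first code late in the 183 days could fail for lack of time. Comparators are also censored at Shingrix vaccination (Section 9.7.6), whereas the primary Dose 1 analysis ignores Dose 2 (Section 9.7.9), so the time available for a second claim could differ by arm. A simple two-claim rule could therefore introduce a bias of its own, and the fix has to deal with this.

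**Conclusion.** The concern holds as a gap in the sensitivity analyses. ION alone can be established by one office claim, its algorithm has no validation figure, and no planned analysis tests the specificity of non-arteritic cases, which Section 9.3.4 indicates are the more common form. The general statement in Section 9.9 that the algorithms have high PPV has no ION figure behind it.

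The possible effect ranges from minor to substantial. With equal false-positive rates and an assumed PPV of 80% down to 30%, a true HR of 2 reads 1.8 down to 1.3. With unequal rates, the estimate can move in either direction. The calculation takes the outcome as rare and the capture of true cases as equal in both arms. An ION result, null or not, would be hard to interpret. Because ION is secondary and has no power target, this is a worthwhile addition and not a threat to the study's main conclusions.

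**What to change.** Keep the one-claim rule as the primary ION definition. Add to Table 3, column 10, a sensitivity definition for all ION:

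- At least two H47.01 claims on different service dates, or at least one inpatient claim with H47.01.
- Onset is the date of the earliest qualifying claim, which must fall within days 1-183 and before censoring.
- The confirming claim may fall within a fixed, prespecified period after the onset date, the same in both arms, even if that is after day 183 or after censoring for vaccination. State this as an exception to the Section 9.3.2 rule that both claims fall within follow-up. Person-time is unchanged.
- The surgical exclusions and the look-back stay as they are.

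Report case counts and rates by arm beside the primary result, subject to the suppression of cells below 11 (Section 10). Fit the primary ION model where case numbers allow, as Section 9.7.7 already provides for the arteritic definition.

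The cost is one additional run on claims already being obtained. For an index date no later than 31 December 2020, day 183 is 2 July 2021, which leaves 182 days of claims before the data end on 31 December 2021. Any later Dose 2 index date would leave less, so the length of the confirming period should be set with that in mind. The downsides are that true cases coded only once are missed under this added definition, that precision is lower, and that death or disenrollment can still prevent confirmation.
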